3.5 Case-control/case-cohort study design

Delete section if not applicable

If, within a cluster, the study population is too large to survey the whole population, a cohort study design on a sample of the population could be carried out, or a case-control or case-cohort study could be undertaken. Also, if the study population of a cluster is not well defined – for example, if the study population is not closed – a case-control or case-cohort study might be carried out rather than a cohort study.

3.5.1 Study population

The study population is defined as the population in which cluster occurs.

3.5.2 Study period

The study period is the duration of the cluster or outbreak as defined by the study team.

This should be detailed in study annexes.

Under certain circumstances the study period could be restricted to part of the duration of the cluster/outbreak if the vaccination status changes substantially during this time period.

3.5.3 Outcome

The primary outcome of interest is laboratory-confirmed pandemic influenza (H1N1) 2009.

Secondary outcomes of interest are:

- persons meeting the EU ILI case definition;
- persons meeting the H1N1 clinical criteria (case definition EU);
- hospitalisations, pneumonia, deaths (or other, if relevant to the cluster).

3.5.4 Cases

Case identification

Information on signs and symptoms of respiratory illness will be collected from all study participants and include:

- cough
- sore throat;
- shortness of breath;
- fever;
- myalgia;
- headache;
- malaise.

All persons presenting with any of those signs and symptoms since the beginning of the cluster should be swabbed.

Mode of specimen collection, storage and transport for each study should be listed in study annexes.

EU ILI definition

A case of ILI is defined as an individual presenting:

- sudden onset of symptoms AND at least one of the following four systemic symptoms:
 - fever or feverishness,
 - malaise,
 - headache,
 - myalgia,
- AND at least one of the following three respiratory symptoms:
 - cough,
 - sore throat,
 - shortness of breath.

Clinical criteria (from EU novel influenza virus A(H1N1) case definition (30/4/2009):

Any person with one of the following three:

- fever > 38°C AND signs and symptoms of acute respiratory infection,
- pneumonia (severe respiratory illness),
- death from an unexplained acute respiratory illness.

Laboratory confirmation

Influenza laboratory confirmation will be done using RT-PCR and/or culture.

☑ RT-PCR characteristics for each study should be listed in study annexes.

Isolates will undergo a molecular analysis for currently circulating influenza A viruses (subtypes H3 and H1) and influenza B. A systematic subset will undergo gene sequencing.

Selection of isolates for each study should be specified in study annexes.

If rapid diagnostic tests (RDTs) are to be used for laboratory confirmation, then their sensitivity and specificity needs to have been studied and documented in a similar situation (e.g. similar study population).

Case inclusion criteria

Cases are eligible if they meet the above case definition and accept to participate.

☑ Oral or written informed consent according to country procedures should be specified in study annexes.

Case exclusion criteria

Cases are excluded if they are not eligible for influenza vaccination because of having a condition listed in the summary of products characteristics (e.g. anaphylactic hypersensitivity to eggs or its components) or if they refuse participation. Reasons for exclusion will be documented.

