3.4.2 Study participants

If the cluster has a manageable population size, the whole study population will be eligible for the VE study. If the population is very large and the attack rate is high, then a systematic or random sample of this population should be selected for the study.

A sample size calculation should be detailed in study-specific annexes.

¹ Orenstein WA, Bernier RH, Dondero TJ, Hinman AR, Marks JS, Bart KJ, et al. Field evaluation of vaccine efficacy. Bull World Health Organ 1985;63(6):1055-68.

Exclusion criteria

Study participants are excluded if they are not eligible for vaccination with the pandemic/seasonal vaccine because of having a condition listed in the summary of products characteristics (e.g. anaphylactic hypersensitivity to eggs or its components), or if they refuse participation. People with laboratory-confirmed diagnosis of A(H1N1)v infection since the beginning of the pandemic (or other date according to the duration of the pandemic) and prior to the beginning of the outbreak/cluster of influenza are excluded as they are not at risk.

People who were not swabbed but had respiratory symptoms in the interval from the beginning of the pandemic (or other date according to the duration of the pandemic) and prior to the beginning of the outbreak/cluster will be documented and analyses carried out including and excluding them.

Reasons for exclusion must be documented.

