3.5.5 Controls

The selection of controls varies according to the nature of the cluster.

Controls must be representative of the source population from which the cases arise in respect to vaccination coverage. In a traditional case-control study, controls who are still disease free (i.e. who did not have A(H1N1)v infection or other outcome of interest) are chosen at the end of the cluster/outbreak. In a case-cohort study, controls are selected from persons who are disease-free at the beginning of the cluster/outbreak. Therefore, persons who got the outcome of interest during the cluster/outbreak can be included as controls. Control selection among people still free of the outcome of interest when a case arises forms a density case-control study.

Controls can be unmatched or matched to cases.

Selection and characteristics of controls should be listed in study annexes.

Control inclusion criteria

Controls are eligible if they meet the above control definition and accept to participate.

☑ Oral or written informed consent according to country procedures should be specified in the study annexes.

Control exclusion criteria

Controls are excluded if they are not eligible for influenza vaccination because of having a condition listed in the summary of products characteristics (e.g. anaphylactic hypersensitivity to eggs or its components) or if they refuse participation. People with laboratory-confirmed diagnosis of A(H1N1)v infection since the beginning of the pandemic (or other date, according to the duration of the pandemic) and prior to the beginning of the outbreak/cluster of influenza are excluded, as they are not at risk.

People who were not swabbed but had respiratory symptoms in the interval from the beginning of the pandemic (or other date, according to the duration of the pandemic) and prior to the beginning of the outbreak/cluster will be documented and analyses carried out including and excluding them.

Reasons for exclusion must be documented.

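### In the case-control design, earlier laboratory-confirmed A(H1N1)v infection excludes controls but not cases, so previously confirmed people can enter only as cases

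*Protocol*

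**What the plan says.** **Cases (Protocol 3.5.4).** Inclusion has two conditions: "Cases are eligible if they meet the above case definition and accept to participate". Exclusion has two grounds. The first is contraindication: "Cases are excluded if they are not eligible for influenza vaccination because of having a condition listed in the summary of products characteristics". The second closes the list: "or if they refuse participation. Reasons for exclusion will be documented". Earlier A(H1N1)v infection is not mentioned.

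**Controls (Protocol 3.5.5).** The same two grounds apply, and a third is added: "People with laboratory-confirmed diagnosis of A(H1N1)v infection since the beginning of the pandemic" (or another suitable start date) and "prior to the beginning of the outbreak/cluster of influenza are excluded, as they are not at risk". The section also sets the standard for choosing controls: "Controls must be representative of the source population from which the cases arise in respect to vaccination coverage".

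**Study population (Protocol 3.5.1).** "The study population is defined as the population in which cluster occurs". There is no restriction to people at risk.

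**Cohort design, for comparison.** Section 3.4.1 limits the population to those at risk of A(H1N1)v. Section 3.4.2 applies the earlier-infection exclusion to every participant: such people "are excluded as they are not at risk".

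**The concern.** In a case-control study, cases and controls should come from the same people: anyone who would be counted as a case on falling ill should be eligible as a control, and the reverse. Here a previously confirmed person who meets the case definition is kept, while a similar person who stays well is removed from the controls. If vaccine uptake differs between people already diagnosed and the rest, coverage among controls no longer describes the population that produced the cases, and the odds ratio moves. Low uptake among the previously diagnosed pushes VE up; high uptake pushes it down. A reader of the results could not tell which had happened.

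This is a core protocol for reuse by many investigation teams, so a gap here is copied into each study that follows it. The cohort and case-control designs would also answer the question in different populations, with no reason given.

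**Working it through.** **Step 1. Does any other section close the gap?**
- 3.5.10 collects earlier confirmed infection from all participants. The exclusion could therefore be applied to cases, but nothing says that it is.
- 3.5.11 has an analysis with and without people who had earlier respiratory symptoms, but only where these were not laboratory-confirmed. Confirmed infection is outside it.
- 4.5 warns in general that including previously ill people may lower VE. It does not mention different rules for cases and controls.
- 3.5.5 leaves the selection of controls to study annexes. 3.5.4 leaves consent, specimen and laboratory details to annexes, but not the exclusion of cases.

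No section extends the exclusion to cases.

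**Step 2. Size of the effect.** The protocol gives no figure on this point, so all inputs are assumptions:
- true VE 50% (RR = 0.5);
- coverage c = 0.5 in people without earlier confirmed infection;
- f = share of the source population previously confirmed;
- v = their coverage, 0.2 or 0.7;
- r = their risk of the outcome relative to other people, among the unvaccinated;
- RRp = vaccine RR among them, 0.5 unless stated.

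Controls are taken as sampled at the start of the cluster, so that the odds ratio estimates the risk ratio. Cases come from everyone, controls only from those without earlier confirmed infection:

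OR = [((1−f)·c·RR + f·v·r·RRp) / ((1−f)·(1−c) + f·(1−v)·r)] ÷ [c/(1−c)], and VE = 1 − OR.

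With c = 0.5 the last divisor is 1.

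- *r = 0, any f and v:* the f terms vanish and OR = RR = 0.5. VE is 50.0%, with no bias.
- *f = 0.05, v = 0.2, r = 0.5:* (0.2375 + 0.0025)/(0.475 + 0.02) = 0.2400/0.4950 = 0.485; VE 51.5%.
- *f = 0.05, v = 0.7, r = 0.5:* 0.24625/0.4825 = 0.510; VE 49.0%.
- *f = 0.20, v = 0.2, r = 0.5:* 0.2100/0.4800 = 0.4375; VE 56.2%.
- *f = 0.20, v = 0.7, r = 0.5:* 0.2350/0.4300 = 0.547; VE 45.3%.

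Range of VE over v = 0.2 and 0.7:

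| Share previously confirmed | r = 0.1 to 0.5 | r = 1 |
|---|---|---|
| 1% | 49.8-50.3% | 49.6-50.6% |
| 2% | 49.6-50.6% | 49.2-51.2% |
| 5% | 49.0-51.5% | 48.0-52.9% |
| 10% | 47.9-53.1% | 45.8-55.7% |
| 20% | 45.3-56.2% | 41.3-60.7% |

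The table assumes the same vaccine effect in both groups. If the vaccine did nothing in the previously confirmed (RRp = 1), the downward bias grows. At v = 0.7 and r = 0.5, VE is 47.2% with f = 5% and 37.2% with f = 20%.

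**Step 3. Which outcomes can have r well above 0?** For laboratory-confirmed A(H1N1)v, r should be small if earlier infection protects. The secondary outcomes in 3.5.3 (EU ILI, the clinical criteria, hospitalisation, pneumonia, death) do not require A(H1N1)v, and the Annex variables for the last three do not tie them to it. For these, r near 1 is plausible, and the right-hand column is the relevant one.

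**Step 4. After the fix.** With the exclusion on both sides, the f terms leave the numerator and the denominator. OR = 0.5 and VE = 50% in every scenario.

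**The case against.** The strongest defence rests on the protocol's own premise. If previously confirmed people are truly not at risk, none can become a laboratory-confirmed case, and a matching case exclusion would remove nobody. Dropping them from the controls is then what makes controls represent the source of the cases. This stands for the primary outcome under full protection, where the calculation gives exactly 50.0%. It does not cover partial protection or the non-specific secondary outcomes, for which 3.5.11 requires separate analyses. The cohort section does not rely on the premise either: it states the exclusion for everyone.

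Second, Section 3.1 looks for clusters in groups with little earlier H1N1 activity, so a confirmed share of 10-20% is high for a suitable cluster. This also stands. It makes the rows up to 5% the more natural ones, although the protocol sets no numerical limit.

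A reader might also infer that the analysis excluding earlier unswabbed symptoms is meant for controls only, because 3.5.5 has that paragraph and 3.5.4 does not. With 30% affected, coverage 20% among them and residual risk 50-100%, VE would then read about 60-65%. The protocol does not support that reading. Section 3.5.11 applies the analysis to persons in general, and 3.5.10 collects the information from all participants.

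**Conclusion.** The point holds as an inconsistency in the eligibility rules. Sections 3.5.4 and 3.5.5 treat earlier confirmed infection differently, 3.5.1 does not restrict the population to those at risk, and the result conflicts with the representativeness rule in 3.5.5 whenever previously confirmed people can become cases and differ in coverage.

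The consequence is modest for the primary outcome. It is nil under full protection. With residual risk 10-50% and the other inputs assumed above, it is at most about 1.5 points with up to 5% previously confirmed and about 6 points with 20%, in either direction. These limits assume the same vaccine effect in both groups. The concern is greater for the secondary outcomes not specific to A(H1N1)v: at equal risk the same inputs give up to about 3 points with 5% and about 11 points with 20%.

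A reader might conclude that the primary VE estimate is necessarily biased, or that the design is invalid. The documents do not support that, because they give neither the share previously confirmed, nor their coverage, nor their residual risk. This is a consistency correction that should be made, not a defect that must stop the plan.

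**What to change.** 1. In 3.5.4, add the exclusion for laboratory-confirmed A(H1N1)v between the start of the pandemic (or other chosen date) and the start of the cluster, in the same words as in 3.5.5.
2. In 3.5.1, define the study population as the population at risk within the population where the cluster occurs, as 3.4.1 does.

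The rule for earlier unswabbed symptoms needs no change, because 3.5.11 already covers all persons.

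The cost is a wording change and possibly the loss of a few cases. The information needed is already collected from all participants under 3.5.10.

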3.5.5 Controls

The selection of controls varies according to the nature of the cluster.

Controls must be representative of the source population from which the cases arise in respect to vaccination coverage. In a traditional case-control study, controls who are still disease free (i.e. who did not have A(H1N1)v infection or other outcome of interest) are chosen at the end of the cluster/outbreak. In a case-cohort study, controls are selected from persons who are disease-free at the beginning of the cluster/outbreak. Therefore, persons who got the outcome of interest during the cluster/outbreak can be included as controls. Control selection among people still free of the outcome of interest when a case arises forms a density case-control study.

Controls can be unmatched or matched to cases.

Selection and characteristics of controls should be listed in study annexes.

Control inclusion criteria

Controls are eligible if they meet the above control definition and accept to participate.

☑ Oral or written informed consent according to country procedures should be specified in the study annexes.

Control exclusion criteria

Controls are excluded if they are not eligible for influenza vaccination because of having a condition listed in the summary of products characteristics (e.g. anaphylactic hypersensitivity to eggs or its components) or if they refuse participation. People with laboratory-confirmed diagnosis of A(H1N1)v infection since the beginning of the pandemic (or other date, according to the duration of the pandemic) and prior to the beginning of the outbreak/cluster of influenza are excluded, as they are not at risk.

People who were not swabbed but had respiratory symptoms in the interval from the beginning of the pandemic (or other date, according to the duration of the pandemic) and prior to the beginning of the outbreak/cluster will be documented and analyses carried out including and excluding them.

Reasons for exclusion must be documented.

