☐ The precise codes used in each study should be specified in study annexes.

Severity

The severity of the underlying conditions will be measured by the number of hospital admissions due to the underlying conditions in the year prior to study inclusion.

Smoking history

Smoking history will be collected and coded as 'never smoked', 'former smoker' (stopped smoking at least one year before inclusion in the study) and 'current smoker'.

Former vaccination

Former vaccination includes:

 Vaccination against influenza in the previous two years (collecting information on vaccination for each of the seasons).

Functional status (where applicable)

Information on functional status will be collected in terms of needing assistance with bathing.

Antiviral administration

Use of antivirals will be documented: type, dose and date of administration.

Other confounding factors that should be considered if available or relevant include:

- Level of social interaction
 - Number of household members
 - Children: nursery vs. school-age children
- Indicators of socio-economic status
 - Education level
 - Profession
 - Others (e.g. deprivation score by area of residence)
- Any other available and relevant for the study population

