3.5.11 Analysis

Analyses will be carried out separately for seasonal and pandemic vaccines and for different vaccine brands.

Separate analyses will be carried out for the different primary and secondary outcomes.

Analyses will be carried out including and excluding persons with recent respiratory symptoms (prior to cluster) that were not lab-confirmed, where information is available.

An analysis will be carried out including only persons 'fully vaccinated' in the vaccinated group. A second analysis will include persons 'fully' and 'partially vaccinated' in the vaccinated group.

Descriptive and univariable analyses

The proportion of eligible ILI cases and controls accepting to participate in the study is calculated (response rate).

Study participants are described by baseline characteristics. Baseline characteristics of cases and controls in unmatched studies are compared using the chi-square test, Fisher's exact test, t-test or the Mann-Whitney test (depending on the nature of the variable and the sample size). In matched case-control studies, characteristics of cases and controls are compared using McNemar's chi-square test, paired t-test, conditional logistic regression or the Wilcoxon signed-rank test (depending on the nature of the variable and the number of controls).

The association between vaccination status and baseline characteristics is assessed for both case and control groups.

Measure of effect

The vaccine effectiveness will be computed as VE = 1 - OR. An exact 95% confidence interval is computed around the point estimate.

Stratified analysis

Analysis will be stratified according to:

- age groups;
- presence or absence of high risk conditions.

A sufficient sample size should be planned in order to ensure sufficient individuals in each stratum. Studies should aim to have at least 80 cases and 80 controls in each of the strata. Effect modification is assessed by comparing the OR across the strata of the baseline characteristics. Confounding is assessed by comparing crude and adjusted OR for each baseline characteristic.

Multivariable analysis

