A multivariable (conditional, if matched) logistic regression analysis will be conducted to control for negative and positive confounding. Odds ratios and standard errors will be obtained. Preferably, the model will include: current influenza vaccination, former influenza vaccination, underlying chronic conditions, age, sex and smoking and functional status. Variables will be tested for multicollinearity. Interactions will be tested for using the Likelihood Ratio test (or Wald test) and included in the model if significant at 5% level. Factors other than statistical significance will also be used as criteria for inclusion of an interaction term.

4 Limitations

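### The density case-control option may be run unmatched and without a time term, so if coverage changes during the outbreak a working vaccine's effectiveness is biased toward zero

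*Protocol*

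**What the plan says.** Section 3.5.5 of the protocol describes three ways of choosing controls. For the third it says: "Control selection among people still free of the outcome of interest when a case arises forms a density case-control study". It then adds, for all three schemes and with no exception for the density design: "Controls can be unmatched or matched to cases". The details go to the individual study: "Selection and characteristics of controls should be listed in study annexes".

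Section 3.5.11 fixes the effect measure ("The vaccine effectiveness will be computed as VE = 1 - OR") and the model: "A multivariable (conditional, if matched) logistic regression analysis will be conducted to control for negative and positive confounding". On model terms it says: "Preferably, the model will include: current influenza vaccination, former influenza vaccination, underlying chronic conditions, age, sex and smoking and functional status". Date and phase of the outbreak are not named there, in the stratification list of 3.5.11, or in the confounder list of 3.5.8. That last list is open, ending with "Any other available and relevant for the study population".

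Section 3.5.2 foresees that coverage may move. It says that under certain circumstances "the study period could be restricted to part of the duration of the cluster/outbreak if the vaccination status changes substantially".

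The Annex lists dates of symptom onset, swabbing and vaccination. It lists no reference date for a control without symptoms, although it allows variables to be added.

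**The concern.** Density sampling works because each case is compared with people still at risk on the same date. The odds ratio within these date-aligned sets estimates the rate ratio without a rare-disease assumption. If controls are treated as unmatched and the model has no time term, sets drawn early at low coverage are pooled with sets drawn late at high coverage, and the alignment is lost. This happens even when every person's vaccination status is read correctly on the sampling date.

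At stake is the VE estimate from any site that takes this route. The bias has a fixed direction for a working vaccine, and a larger sample does not reduce it. Changing coverage is foreseeable: the Background wants estimates as soon as possible once the pandemic vaccine is available, and 3.5.2 anticipates a substantial change in vaccination status during an outbreak.

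**Working it through.** **Figures in the protocol.** The protocol gives no coverage trajectory and no figure for this bias. Its Table 6 does allow a check of the relation between coverage in controls and in cases that is used below. With control coverage p and odds ratio OR, coverage in cases is

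q(p) = p·OR / (1 − p + p·OR).

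For the Table 6 row with coverage 50%, OR 0.5 and power 0.80, q = 0.25/0.75 = 0.3333. The two-sided 5% comparison of 0.3333 with 0.50 needs 136.2 per group before and 147.9 after continuity correction; the table states 148. All 24 rows reproduce to within 1 with the correction.

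**Direction.** The second derivative of q(p) is 2·OR·(1 − OR) / (1 − p + p·OR)³, which is positive for OR < 1. Case coverage averaged over time is therefore at least q at the average control coverage, and more than that whenever coverage varies. The pooled estimate is

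pooled OR = odds(mean q) / odds(mean p),

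so it lies above the true OR. Since q < p at every date with some but not full coverage, it stays below 1. VE thus moves toward zero but does not change sign. With OR = 1, q = p and there is no bias; with constant p there is none either.

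**Assumptions for size.** True OR constant over time; a constant number of controls per case; status read correctly at each date; no other confounding. The OR range of 0.3 to 0.6 is that of Table 6. All coverage paths are assumptions. The 50-70% range is taken from Table 6, which gives it as alternative scenarios and not as a rise over time.

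**Three examples: true OR 0.5 (VE 50%), two periods, half the cases in each.**

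| Control coverage | Case coverage | Mean q | Mean p | Pooled OR | VE | Loss (points) |
|---|---|---|---|---|---|---|
| 50% / 70% | 0.3333 / 0.5385 | 0.4359 | 0.60 | 0.7727/1.5 = 0.515 | 48.5% | 1.5 |
| 10% / 40% | 0.0526 / 0.2500 | 0.1513 | 0.25 | 0.1783/0.3333 = 0.535 | 46.5% | 3.5 |
| 10% / 70% | 0.0526 / 0.5385 | 0.2955 | 0.40 | 0.4195/0.6667 = 0.629 | 37.1% | 12.9 |

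**Loss in VE points over true OR 0.3 to 0.6.**

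| Coverage | Two-period step | Linear rise, flat epidemic curve | Linear rise, bell-shaped curve (SD 0.2 of the outbreak) |
|---|---|---|---|
| 50 to 70% | 1.3-1.6 | 0.4-0.5 | 0.2 |
| 10 to 40% | 3.1-3.5 | 1.0-1.2 | 0.4-0.5 |
| 10 to 70% | 11.5-13.4 | 3.7-4.2 | 1.6-1.8 |
| 0 to 70% | 16.5-19.1 | 5.2-5.9 | 2.2-2.5 |

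**Does keeping the time alignment remove it?** In a simulation of 200,000 case-control pairs with true OR 0.30 and coverage rising linearly from 10% to 70%, the crude OR was 0.343, the OR adjusted for time 0.304 and the 1:1 conditional OR 0.303. With true OR 0.40 and a rise from 10% to 50%, the three were 0.421, 0.402 and 0.402. The remaining differences from the true OR are simulation error.

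**The case against.** The best defence is that the plan does not prescribe the biased analysis. A density control is chosen when its case arises, so a team may well regard its sets as matched on date, and 3.5.11 would then lead it to conditional regression. The matching sentence can be read as concerning further factors such as age or sex. The lists of model terms and confounders are open, and this is a core template that sends control selection to study annexes. All of this stands, and it is why the point is about a permission. It does not remove the point: the sentence on matching makes no exception for the density design, and nothing tells a local team that date must be kept.

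Section 3.5.2 is a real, if partial, safeguard, since it targets the steep changes that give the largest losses. It is optional, sets no threshold and discards cases, although 3.5.8 (Sample size) and 4.1 warn that numbers are often fixed and low. Matching on date keeps every case.

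A reader might infer that the plan as written costs 3 to 13 points of VE. The documents do not support that as a general range. It needs an abrupt step from 10% to 40% or up to 70%, with half the cases on each side. A reader might also infer that every VE estimate under this protocol is affected. The problem reaches only a site that chooses case-control, then density sampling, then an unmatched analysis without time, while coverage changes.

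**Conclusion.** The point holds as a permission that should be closed. As worded, 3.5.5 and 3.5.11 allow an unmatched density analysis that pools over sampling dates. For an effective vaccine and changing coverage, its VE is biased toward zero.

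Under the assumptions listed, the loss is:

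- about 0.2 to 1.6 points for coverage moving within 50-70%;
- about 1.6 to 4.2 points for a gradual rise from 10% to 70%;
- about 3 to 13 points for two-period steps from 10/40% to 10/70%;
- zero with stable coverage or a vaccine without effect.

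A larger step can exceed 13 points. The protocol gives no coverage path, so none of these figures can be called the expected loss. The importance is modest, but the correction is cheap and removes the bias.

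**What to change.** - **3.5.5:** state that density controls are always matched to their case on date, with vaccination status read at the case's onset date, and that the choice between unmatched and matched concerns other factors only.
- **3.5.11:** for the density design, require conditional logistic regression on the date-matched sets. If the sets are broken, require onset or sampling date in the model in categories, for example by week.
- **Annex:** add a reference date for each control.

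The cost is a sentence or two in each section, one extra variable to record, and a slightly wider confidence interval from conditioning on date. That widening should be small where coverage is stable.
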